1.0 PROTOCOL SUMMARY AND/OR SCHEMA

Title: A Pilot, Prospective, Randomized, Double-Blinded, Vehicle- and Comparator-Controlled Trial on Safety and Efficacy of a Topical Inhibitor of Janus Kinase 1/2 (Ruxolitinib INCB018424 Phosphate 1.5% Cream) for Non-Sclerotic and Superficially Sclerotic Chronic Cutaneous Graft-Versus-Host Disease (GVHD).

Total Study Follow-up per patient: 56 days

Schema

2.0 OBJECTIVES AND SCIENTIFIC AIMS

Primary Objective:

- To obtain preliminary efficacy estimates of ruxolitinib 1.5% cream for the treatment of non-sclerotic and superficially sclerotic chronic cutaneous GVHD at day 28 as determined by the body surface area (BSA) of the GVHD rash on the side of the face/body treated with topical ruxolitinib cream versus contralateral side treated with vehicle at day 28 visit when applied beginning on day 1.

Secondary Objectives:

- To obtain preliminary efficacy estimates of ruxolitinib 1.5% cream for the treatment of non-sclerotic and superficially sclerotic chronic cutaneous GVHD at day 28 as determined by the Physician's Global Assessment of Clinical Condition (PGA) of the

MEMORIAL SLOAN KETTERING CANCER CENTER IRB PROTOCOL

GVHD rash on the side of the face/body treated with topical ruxolitinib cream versus contralateral side treated with vehicle at day 28 visit when applied beginning on day 1.

- To obtain preliminary efficacy estimates of ruxolitinib 1.5% cream for the treatment of non-sclerotic and superficially sclerotic chronic cutaneous GVHD at day 28 as determined by the objective Composite Assessment of Index Lesion Severity (CAILS) of the GVHD rash on the side of the face/body treated with topical ruxolitinib cream versus contralateral side treated with vehicle at day 28 visit when applied beginning on day 1.
- To obtain preliminary efficacy estimates of ruxolitinib 1.5% cream for the treatment of non-sclerotic and superficially sclerotic chronic cutaneous GVHD at day 14 as determined by the body surface area (BSA), Physician's Global Assessment of Clinical Condition (PGA), and the objective Composite Assessment of Index Lesion Severity (CAILS).
- Compare the difference in patient-reported outcomes between the side of the face and body treated with topical ruxolitinib cream versus the contralateral side treated with twice daily vehicle at day 14 visit and day 28 visit using the adapted National Cancer Institute Patient-Reported Outcomes version of the Common Terminology Criteria for Adverse Events (PRO-CTCAE™) questionnaire
- Compare the difference in chronic cutaneous non-sclerotic and superficially sclerotic GVHD BSA between the sides of the face/body treated with topical ruxolitinib and vehicle by measuring the agreement of blinded independent physician's review of standardized photography of the right and left sides of the face and body respectively performed at day 28 visit
- Assess the safety and tolerability of topical ruxolitinib by physical examination and adverse event reporting
- To evaluate accrual, retention and compliance with therapy
- To describe molecular expression profiles of lesional GVHD skin at baseline and after treatment with topical ruxolitinib or vehicle moisturizer via minimally invasive skin tape strip RNA sequencing

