8.0 PRETREATMENT EVALUATION

Patients may be screened and consented starting from up to 7 days before study initiation.

The following initial baseline procedures can take place at any time during this period, or on the day of initiation (Day 1)

1. Medical history, including concomitant medications
2. Study assessments (serve as baseline measures for the study):
 - Patient-reported Outcomes (Appendix III):
 - Adapted PRO-CTCAE™ for each side of face/body affected by GVHD rash
 - Clinical assessments (Appendices I, II, IV, V)
 - Skin examination with calculation of body surface area (BSA), Physician's Global Assessment of Clinical Condition (PGA), and the objective Composite Assessment of Index Lesion Severity (CAILS) for each side
 - Standardized photography and 3D photography
 - During the first and third study visit, if the participant gives consent, the research photographer will take 3D photography, also called Total Body Photography of the patient.

MEMORIAL SLOAN KETTERING CANCER CENTER IRB PROTOCOL

- For each side, the skin area targeted for treatment will be outlined with surgical marker, photographed, and a photograph of each outlined target treatment area will be provided to the patient as an application reference.
- Laboratory investigations
 - Laboratory analyses and skin biopsy will be performed only as clinically indicated for routine care.
 - Minimally invasive skin tape strip RNA sequencing will be performed on each face/body side by the study dermatologist (Appendix VIII)

Visit # Study day:	Pre-study Screening or Day 1
Reason for visit	
Informed consent	X
Medical history	X
Pregnancy test (if applicable for females of child-bearing potential)	X
Clinical assessment (i.e., BSA, PGA, and CAILS on each side; adverse events/CTCAE assessment)	X
Skin examination	X
Lesional skin tape stripping on each side	
Patient-reported outcomes questionnaire for each side	X
Standardized photography	X
Drug application	X
Drug diary return	X
Drug accountability	X

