10.0 EVALUATION DURING TREATMENT/INTERVENTION

Table 1. Assessments: 4 to 5 study visits

Visit #	Pre-study	1	2	3	4	5	6
Study Day	Day -7 to Day 0	Day 1	Day 14 ± 3 days	Day 28 ± 3 days	Day 56 ± 5 days	Day 84 ± 5 days	28 Days ± 5 days after treatment completion
Reason for visit	Screening	Pre-treatment baseline evaluation	Interval follow-up evaluation	Blinded Treatment ends	Safety follow-up visit/Open label extension follow-up evaluation	Open-label extension safety follow-up visit	Safety follow-up visit after treatment extension period ends
Informed consent	X				X****		
Medical history	X						
Pregnancy test (if applicable for females of child-bearing potential)	X			X			
Clinical assessment (i.e., BSA, PGA, and CAILS on each side; adverse events/CTCAE assessment)		X	X	X	X	X	X
Skin examination		X	X	X	X	X	X
Lesional skin tape stripping on each side				X			
Patient-reported outcomes		X	X	X	X	X	X

MEMORIAL SLOAN KETTERING CANCER CENTER
IRB PROTOCOL

questionnaire for each side							
3D Photography**		X		X			
Standardized photography		X	X	X	X	X	X
Drug application		X	X	X	X***		
Drug diary return			X	X			
Drug accountability			X	X	X***		

* Day 1 assessments can also be done at day 0

** Optional for the study. Participant does not need to complete in order to participate on the study.

*** For those patients who enroll onto open label portion, but do not enroll into the extension period of the study: patients apply study drug up to Visit 4 but not after this visit. Patients who enroll into the extension period will continue to apply drug until they withdraw from the extension period.

****For patients who enroll into treatment extension period.

For study purposes, Study Day 1 is defined as the first day of topical application.

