- **Safety follow-up:** After completion of the 28 day ± 3 days study interval, patients will return for a final safety and follow-up visit at day 56 ± 5 days. Additionally, any patients who repeat a study drug course will return for an additional safety visit at day 84 ± 5 days. At this visit, patients will have a safety evaluation for possible adverse events (Table 1).
- **Diagnostic interventions:** Laboratory analyses and skin biopsy will be performed as clinically indicated. Minimally invasive skin tape strip RNA sequencing will be performed on each face/body side by the study dermatologist on study visit on day 28 ± 3 days. These skin strips will be shipped to DermTech, Inc. ([name]) Appendix VIII)
- Compliance with the topical agent will be assessed by reviewing the patient's application diary (Appendix VII).

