sclerotic GVHD BSA between the sides of the face/body treated with topical ruxolitinib and vehicle by measuring the agreement of blinded independent physician's review of standardized photography of the right and left sides of the face and body respectively performed at day 28 visit; (6) The safety and tolerability of topical ruxolitinib by physical examination and adverse event reporting; (7) Accrual, retainment and compliance with therapy

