13.0 CRITERIA FOR REMOVAL FROM STUDY

Patients will be removed from the study (and will not be replaced) if:

- They develop an adverse event necessitating discontinuation of topical interventions.
- They require greater than 14 days off therapy due to a treatment-related adverse event.

Patients will be removed from the study and replaced if:

- They enroll in an alternate systemic clinical trial which prohibits concurrent topical clinical trial participation.
- They choose to withdraw consent for continued participation.
- Death occurs.

All patients who receive ruxolitinib and report using the treatment will be evaluable for toxicity.

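### The molecular objective and section 8.0 call for baseline tape strips, but Table 1 and section 10.2 schedule them only at day 28

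*Combined protocol and SAP*

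**What the plan says.** Five places bear on the timing of the tape strips.

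- **Section 2.0, last secondary objective.** The aim is to describe "molecular expression profiles of lesional GVHD skin at baseline and after treatment with topical ruxolitinib or vehicle moisturizer". It names two time points and does not say which side is to be sampled at baseline.
- **Section 8.0, text.** The list opens with "The following initial baseline procedures can take place at any time during this period, or on the day of initiation (Day 1"). Under laboratory investigations it includes "Minimally invasive skin tape strip RNA sequencing will be performed on each face/body side by the study dermatologist (Appendix VIII"), with no other date.
- **Section 8.0, table.** The only column is for screening or Day 1. The tape-strip row is empty.
- **Section 10.0, Table 1.** Visit 1 is headed "Pre-treatment baseline evaluation". The row "Lesional skin tape stripping on each side" is marked once, at Visit 3 (day 28).
- **Section 10.2.** Tape strip sequencing will be "performed on each face/body side by the study dermatologist on study visit on day 28 ± 3 days". No other visit is given.

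Sections 8.0 and 10.2 both refer to Appendix VIII for the stripping instructions. Its text is not among the documents reviewed. Section 14.0 promises descriptive statistics for the molecular profiles and gives no time point.

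**The concern.** The objective needs a pre-treatment profile, but the visit schedule does not ask for one. Table 1 is the schedule that clinic staff are likely to follow. If they do, the first tape strip is taken after 28 days of treatment.

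This cannot be repaired later, because Study Day 1 is by definition the first day of application. The routine data quality reports in section 16.1 might expose the gap, but they cannot restore samples from patients already treated.

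Without a baseline sample, the molecular data would support only a comparison of the ruxolitinib side with the vehicle side at day 28. Change within a side could not be described, and the baseline half of the objective would go unmet.

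**Working it through.** The plan gives no figure to reproduce. The check is a comparison of the texts and a count of table cells.

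**1. Time points by source**

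| Place | Baseline | Day 28 |
|---|---|---|
| Section 2.0 objective | Yes | After treatment, no day given |
| Section 8.0 text | Yes, each side | Not addressed |
| Section 8.0 table | Row present, cell blank | No such column |
| Table 1 | Pre-study and Visit 1 blank | Marked |
| Section 10.2 | Not mentioned | Yes, each side |

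**2. Position of the mark in Table 1.** Seven cells follow the row label: Pre-study and Visits 1 to 6. The tape-strip mark is in the fourth, which is Visit 3. Other rows keep their columns: the pregnancy test is marked at Pre-study and Visit 3, and 3D photography at Visits 1 and 3. The optional 3D photography therefore has the baseline-plus-day-28 pattern that the molecular objective needs and the tape-strip row lacks.

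**3. Section 8.0 table.** Leaving out the row for the reason for visit, there are 11 procedure rows. Ten are marked; tape stripping is the only one that is not. A mark lost when the PDF was read cannot be excluded, so this is supporting evidence only.

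**4. Section 10.2 compared with itself.** It names day 1 for BSA, PGA, CAILS and the patient-reported outcomes, but not for tape strips.

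**5. Samples at risk**

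- Each side sampled, as the section 8.0 text says: 2 sides × 24 patients = 48 side-level samples.
- One side sampled, since the objective names none: 1 × 24 = 24.
- Gap noticed only at the first interim analysis, after 10 evaluable participants: 2 × 10 = 20 already lost, plus any from other patients treated by then.
- Section 13.0 has a list headed "Patients will be removed from the study and replaced if"; each replacement could add up to 2.

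These are samples, not strips. The documents do not give the number of strips per sample.

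**6. Reach into the analysis.** Molecular profiles are in neither list of secondary outcomes. The section 12.0 list stops at "7) Accrual, retainment and compliance with therapy", and the seven numbered endpoints in section 14.0 do not include them. Their only analysis statement is descriptive, so no planned test depends on the baseline strip.

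**The case against.** The best defence is that section 8.0 covers what happens before treatment and section 10.2 what happens during it, so together they mean baseline plus day 28. Section 10.2 does not exclude a baseline strip, and this reading is possible. It is strained, because section 10.2 does list day 1 for the other assessments. Even if accepted, it leaves Table 1 without the baseline mark.

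A second argument is that the objective and the section 8.0 text may be the outlying passages, since both tables and section 10.2 agree with each other. That stands as a point about intent, which the documents do not settle. It is why two remedies are offered, but it does not remove the conflict.

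Third, the blank cells might be extraction faults, and the section 8.0 table is uneven evidence: it marks diary return and drug accountability at screening or Day 1, where Table 1 does not. This weakens the section 8.0 table as evidence. It does not account for section 10.2, which is prose and names only day 28.

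Fourth, Appendix VIII may state the timing. It may, but Table 1 would still need correcting.

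Finally, 48 is a ceiling. It assumes that no baseline strip is taken from any patient, despite an instruction to the study dermatologist in section 8.0. The 24-sample case has little support, because both tables and sections 8.0 and 10.2 all say each side. Both remarks are fair and limit the size of the problem, not its existence.

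**Conclusion.** The concern holds. The objective and the section 8.0 text require a baseline tape strip; Table 1 does not schedule one, and section 10.2 names only day 28. If Table 1 is followed as printed, up to 2 pre-treatment side-level samples per patient are lost for good, with a ceiling of 48 over 24 patients before any replacements.

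The consequence is limited to the baseline part of one descriptive secondary objective. The BSA primary endpoint, the sample size, the day-28 comparison of sides and every planned test are unaffected. It should still be corrected, because the loss cannot be reversed.

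The conclusion rests on the sections reviewed, with Table 1 read by column position, and assumes that staff schedule visits from that table. Any timing in Appendix VIII could not be checked.

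**What to change.** Reconcile sections 2.0, 8.0, 10.0 (Table 1) and 10.2, and check Appendix VIII against the result. There are two ways to do so.

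1. **Keep the baseline profile.** Mark tape stripping before the first application, at screening or Day 1, in Table 1 and in the section 8.0 table, and add that time point to section 10.2. If the baseline strips in the section 8.0 text are already budgeted, this changes only the wording of the schedule. The documents give no tape-strip budget; if they are not budgeted, the cost is up to 48 further side-level samples to collect and sequence for 24 patients.
2. **Drop the baseline profile.** Delete the tape-strip bullet and the unmarked row from section 8.0, and restrict the objective to the side-to-side description at day 28. This needs no extra sampling, but it gives up a stated part of the objective and so is a substantive amendment.

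The first option preserves the objective as written. The choice should be made before further patients start treatment.

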3.0 BACKGROUND AND RATIONALE

Non-sclerotic and superficially sclerotic chronic cutaneous graft-versus-host disease (cGVHD)

In 2016, Memorial Sloan Kettering Cancer Center Bone Marrow Transplantation Service performed 233 adult and 33 pediatric allogeneic hematopoietic stem cell transplantation (HCTs). Approximately 30-40% of the unmodified allograft recipients are expected to develop chronic GVHD (cGVHD). The skin is the most common site of cGVHD involvement (~75% of patients have cutaneous cGVHD)[1].

Classic chronic GVHD is diagnosed (and distinguished from aGVHD) by the presence of at least one diagnostic clinical manifestation (any of: poikiloderma, lichen planus-like features, keratosis pilaris-like features, maculopapular rash/erythema, deep sclerotic-like features, morphea-like features, lichen sclerosus-like features) OR at least one distinct manifestation (any of: depigmentation, sweat impairment, ichthyosis, keratosis pilaris, hypopigmentation, hyperpigmentation, etc) confirmed by pertinent biopsy or other relevant test (Table 2). Sclerotic

MEMORIAL SLOAN KETTERING CANCER CENTER IRB PROTOCOL

subtypes of chronic cutaneous GVHD includes deep sclerotic and superficially sclerotic subtypes (lichen sclerosus-like, morphea-like subtypes). Deep sclerotic cGVHD will be excluded from this study.

Chronic GVHD is the leading cause of nonrelapse mortality in patients surviving more than 2 years after allogeneic HCT with negative impact on quality of life and long-term outcomes[2]. While transplant practices have advanced over the last decades, the incidence and severity of cGVHD have continued to rise[2, 3]. Of organs affected by cGVHD, severe skin involvement has increased in recent years (from 51% of patients with cutaneous cGVHD at maximum severity in 1999, 65% 2003, and 71% in 2007[3]. Median onset of cGVHD is 4 to 6 months after allogeneic HCT, with 5-10% of cases diagnosed beyond 1 year[1]. The clinical manifestations of cGVHD are variable, and half of patients have 3 or more involved organs[1]. Median duration of cGVHD treatment is 2-3 years; however 15% of patients required treatment after 7 years[1].

Diagnostic (Sufficient to establish the diagnosis of chronic GVHD)	Distinctive (Seen in chronic GVHD, but insufficient alone to establish a diagnosis of chronic GVHD)	Other Features (Can be acknowledged as part of the chronic GVHD symptomatology if the diagnosis is confirmed)	Common (Seen with both acute and chronic GVHD)

 • Poikiloderma • Lichen planus-like features • Morphea-like features • Lichen sclerosus-like features • Sclerotic features 	
 • Depigmentation 	
 • Sweat impairment • Ichthyosis • Keratosis pilaris • Hypopigmentation • Hyperpigmentation 	
 • Erythema • Maculopapular rash • Pruritus

Current treatment recommendations

To date, there have been no randomized, controlled trials evaluating topical therapies for cutaneous cGVHD, nor are there any FDA-approved topical treatments.

Despite this lack of evidence, topical corticosteroids are the mainstay of mild chronic GVHD therapy[4-6]. As supported by case reports, topical calcineurin inhibitors (i.e., pimecrolimus cream, tacrolimus ointment) are used with variable efficacy in areas at greatest risk for topical corticosteroid side effects such as the intertriginous areas and face, as well as for patient who have developed steroid dependence[4, 5, 7, 8]. However, in one case series of 18 patients with cutaneous cGVHD treated with topical tacrolimus 0.1% ointment twice daily, all patients eventually went on to receive more aggressive treatment including increases in steroid dosage, psoralen-ultraviolet-A (PUVA) therapy, or extracorporeal photophoresis[7]. Emollients are also recommended as topical management for chronic cutaneous GVHD by the Ancillary Therapy and Supportive Care Working

MEMORIAL SLOAN KETTERING CANCER CENTER IRB PROTOCOL

Group[4]. For cutaneous cGVHD with extensive body surface area, skin-directed therapies include ultraviolet A and narrowband ultraviolet B phototherapy[4], which are associated with increased risk for skin cancer (including squamous cell carcinoma, basal cell carcinoma, and melanoma).

Chronic cutaneous non-sclerotic and superficially sclerotic GVHD may be topical- or systemic steroid- dependent/ refractory, prompting additional immunosuppressive systemic therapies or extracorporeal photophoresis/phototherapy. No topical therapies have been approved, and off label use of topical corticosteroids and topical tacrolimus are mainstays of therapy, despite limited efficacy and established side effects. Topical corticosteroid use increases risk for development of localized infections, striae, skin atrophy/thinning, bruising, acne, discoloration, dependence and with widespread use: hyperglycemia, adrenal suppression, and moon-facies [9]. Erythema, burning, edema may be experienced on discontinuation of long-term topical steroid use[10]. Half of patients experience a burning sensation upon application of topical calcineurin inhibitors. Given the variable efficacy and adverse event profile of currently available topical and systemic therapies for chronic cutaneous GVHD, there is an unmet need to have new options for anti-inflammatory treatment in this patient population.

Systemic Janus kinase inhibitors and Graft-versus-host disease

Janus kinase (JAK) are intracellular nonreceptor tyrosine kinases which play critical functions in T-cell activation, inflammation, and tissue damage and predicted to be involved in the pathogenesis of GVHD [11, 12]. JAK inhibitors, including ruxolitinib (JAK 1/2 inhibitor) and tofacitinib (JAK 1/3 inhibitor), inhibit the signal transduction and activation of transcription (STAT) pathway that is essential for downstream growth factors and inflammatory cytokines[5].

JAK inhibitors' anti-inflammatory properties have been investigated in several immunopathogenic disorders. Systemic ruxolitinib is a potent oral selective JAK1/JAK2 inhibitor with equipotent activity toward JAK1 and JAK2[12] and has been approved by the FDA for the treatment of intermediate or high-risk myelofibrosis, including primary myelofibrosis, post polycythemia vera myelofibrosis and post essential thrombocythemia myelofibrosis, and patients with polycythemia vera who have had an inadequate response to or are intolerant of hydroxyurea[12]. Systemic ruxolitinib has demonstrated efficacy for management of acute and chronic GVHD in animal models as well as in patients with GVHD in several small studies and retrospective clinical reports[11, 12]. However, the systemic use of ruxolitinib is associated with several adverse events including anemia, thrombocytopenia, neutropenia, liver dysfunction, diarrhea and infection risk that could limit a broader use, particularly in allo-HCT recipients with GVHD who commonly have cytopenias, GI and hepatic dysfunction.

Topical ruxolitinib (JAK 1/2 inhibitor)

While not commercially available, the topical JAK inhibitors ruxolitinib (JAK 1/2 inhibitor) and tofacitinib (JAK 1/3 inhibitor) have been investigated for management of alopecia areata[13], vitiligo, psoriasis and atopic dermatitis with efficacy[14-16].

In patients with active psoriasis, topical ruxolitinib (INCBO18424) 1.5% cream twice daily for 28 days was pharmacologically active, modulated proinflammatory cytokines, and was well tolerated; treatment resulted in improvements in psoriasis lesion scores[17]. No significant inhibition of pSTAT3 in peripheral blood cells was observed following topical application, consistent with the

**MEMORIAL SLOAN KETTERING CANCER CENTER
IRB PROTOCOL**

generally low steady-state plasma concentrations of INCB018424 measured[17]. A 20-week, open-label, proof-of-concept trial of twice daily topical ruxolitinib 1.5% cream in 12 patients provided significant repigmentation in facial vitiligo[18]. A topical JAK/spleen tyrosine kinase (SYK) dual inhibitor has demonstrated efficacy for ocular GVHD with a higher mean decrease in total corneal fluorescein staining in the group treated with an ophthalmic JAK/SYK solution as compared to the vehicle-treated group at 12 weeks [19].

Topical ruxolitinib and chronic cutaneous non-sclerotic and superficially sclerotic GVHD

Given efficacy of ruxolitinib with oral use in GVHD and with topical use in other dermatoses, we hypothesize topical ruxolitinib may be used for the treatment of chronic cutaneous (non-sclerotic) and superficially sclerotic (lichen sclerosus-like; morphea-like) GVHD and will be more effective in decreasing the body surface area of chronic cutaneous GVHD when compared to topical vehicle.

Of note, topical ruxolitinib treatment in a murine model of skin GVHD was associated with less severe skin GVHD scores, reduced T-cell infiltration of the skin and maintenance of LGR5+ hair follicle stem cell levels that are normally reduced with the onset of GVHD[12, 20, 21]. Skin GVHD targets Lgr5+ hair follicle stem cells in association with impaired hair regeneration and wound healing[20]. Topical ruxolitinib, unlike corticosteroids, protects Lgr5+ skin stem cells and maintains skin homeostasis in skin GVHD[20].

This study utilizes a novel method of delivery and active agent for the topical treatment of cutaneous GVHD, potentially expanding the therapeutic options for patients with GVHD. Topical ruxolitinib would augment the armamentarium of agents available to treat these patients, without resorting to systemic immunosuppressive therapies, nor causing side effects of skin atrophy, bruising, and tachyphylaxis due to topical steroids.

